The aim of the present study is to evaluate whether it is safe with regard to surgical complications to offer early breast cancer patients a possibility to preserve the native breast skin with a minimally invasive procedure at a very critical time in the patient pathway. Thus, more extensive reconstructive procedures may be postponed to a less critical point of time in the woman's life.

The present study will add valuable prospectively collected data, to the DBCG population-based database on reconstructive procedures, morbidity, and final outcomes after reconstruction and PMRT.

The protocol for the current study has been changed as of June 2023 from a randomized controlled trial to a prospective study, due to unexpected low accrual (see below).

It is expected that the delayed-immediate reconstructive procedure will become the new DBCG recommendation for patients operated with mastectomy and who will have PMRT. The decision will be made by the DBCG Surgical and Radiation Therapy Committees when the first results are available. Evaluation of morbidity in the accrued patients will continue for 10 years, and if the results at a later time point are not in harmony with the first results, the recommendation in the DBCG guidelines may be altered. The DBCG Surgical and Radiation Therapy Committees decide that.

Hypothesis

Delayed-immediate breast reconstruction does not increase the risk of complications compared with the conventional delayed reconstruction in patients who are to have post-mastectomy radiation therapy.

Aim

The aim of the present trial is to monitor the occurrence of complications after delayed-immediate breast reconstruction, and compare this with delayed reconstruction in breast cancer patients with post-mastectomy radiation therapy. In addition, patient-reported outcomes will be evaluated postoperatively and compared to preoperative measurements.

STUDY POPULATION

Inclusion criteria

- Woman >18 years who are offered a mastectomy for invasive breast can-

cer pT1-3, pN0-N3, M0 and wish reconstruction. The patient can be included no matter the status of estrogen receptor, progesterone receptor, malignancy grade, and HER2 status.

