The patient can be included irrespective of the type and timing of systemic therapy. This trial accepts that randomized patients participate in other trial protocols testing new systemic therapies, e.g. inhibitors of CDK4 and CDK6 kinase activity like abemaciclib in the Monarch E trial. It is also accepted that the patient is included in trials testing loco-regional therapies, e.g. the SENOMAC trial and the

Skagen Trial 1.

TREATMENT PROTOCOL

The first version of the trial was designed as a randomized trial. The inclusion started 1/1-2020. Due to slow accrual, the steering committee has decided to change the trial per 30/6-2023 to a prospective trial of arm A without randomization. It is expected that a prospective trial design will make it feasible for more departments to participate

Treatment arm A

Delayed-immediate reconstruction:

Primary Surgery: Skin sparing mastectomy (nipple sparing if appropriate) and axillary surgery according to guidelines or protocol. Reconstruction with silicone implant or expander covered by pectoral muscle and mesh or matrix.

Delayed reconstruction: Final reconstruction with any reconstructive procedure – being it autologous or implant-based (one- or two-stage, +/- acellular dermal matrix (ADM)) – is performed 6-12 months after completion of chemotherapy and RT. Any contralateral procedure is allowed when doing the delayed surgery, but not in relation to the initial cancer surgery.

Patients, who will not have the second delayed procedure performed will be included in the analysis of 'intention to treat' group and not excluded from the study.

Treatment arm B

Delayed reconstruction:

Primary surgery: Total mastectomy and axillary surgery according to guidelines or protocol.

Delayed reconstruction: 6-12 months after completion of PMRT: final reconstruction with any reconstructive procedure – being it autologous or implant-based (one-or two-stage, +/- ADM). Any contralateral procedure is allowed at any time point after PMRT has been delivered.

This arm recruited patients between 1/1-2020 and 30/6-2023

Concerning post mastectomy radiation therapy (PMRT)

This issue is described in the new ESTRO consensus guidelines for target volume delineation in implant based reconstruction ²⁶.

In general, the tissue beneath the skin surface of the mammarian region is the clinical target volume in all cases.

Implant-based reconstruction and PMRT

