Consequently, patients accepting participation in this study should be informed that reconstruction in combination with radiotherapy after mastectomy at least doubles the risk of surgical complications but does not increase the risk of dying of breast cancer. It is not expected that the new reconstruction method will increase the complication rate compared to standard reconstruction methods in combination with radiotherapy after mastectomy. The study is designed to show that the patients in the interventional study group will not have a risk exceeding 36% for surgical complications needing further surgery.

INFORMATION OF THE PATIENT

Information is given in the plastic surgery clinic when patients are informed about the diagnosis and the treatment plan is discussed with her. The meeting takes place in a quiet and undisturbed room. The informing doctor first informs the patient about the standard therapy with total mastectomy, radiotherapy and delayed reconstruction, and it will be made clear to her that this is the standard therapy. Then the doctor informs about the possibility of participating in the trial with delayed-immediate reconstruction. The patient is informed about the pros and cons of proceeding with delayed-immediate breast reconstruction and subsequent radiation therapy. This treatment is only offered as part of this study, and not outside the trial. In the period with randomized trial design the patient was in addition informed about randomization between standard therapy and experimental therapy. The patients will be informed according to the national guidelines regarding patient participation in trials. The patient is handed a written information about both standard therapy and the therapy on trial. The patient is invited to give her consent after she has had sufficient time to make her decision, and she is offered another session at the hospital to give her consent to participate in the trial after a 24 hour time of reflection. She is encouraged to

have an observer present, when giving her consent. After her written consent, baseline morbidity evaluation is performed,

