At the first consultation and in the written information about the trial the patient is informed that we want information from her patient file passed on to the trial regarding tumour characteristics, and also about her recurrence and survival status for 15 years after randomization and on events related to the reconstruction. If she has a recurrence we need data passed on from her patient file regarding when and where the recurrence took place. The tumour characteristics are: tumour histological type, size, lymph node status (how many removed and how many with metastasis and what type of metastasis), malignancy grade/ER/PR/HER2/Ki67 status, Q score, resection margin, and surgical procedure, radiation therapy, and systemic treatment. Also information about serious events like a new cancer, heart disease, lung disease and stroke is passed on from her patient file, because these events may be related to the radiation therapy. If an increased risk of any of these events is associated with one of the radiation therapies on trial, it will influence the decision on what is to be future standard therapy.

The patient will be informed that the consent provides the investigators of the study direct access to obtain the necessary information from medical records to conduct the investigation and follow-up.

OUTCOME

Primary endpoint

Any complication deeming *surgical intervention* necessary (excluding percutaneous drainage and antibiotic treatment for inflammation in cases without need for open drainage) within a period up to 1 year after the final reconstruction:

- Infection
- Hematoma
- Loss of implant/expander
- Necrosis
- Seroma

Secondary endpoints

- Necrosis not requiring surgical intervention
- Infection not requiring surgical intervention but antibiotic treatment
- Herniation at donor-site
- Patient's satisfaction and QoL evaluated by BREAST-Q – appropriate modules.
- Psycho-oncological endpoints evaluated by validated questionnaires:
 - Depression (Becks Depression Inventory, BDI)
 - Fear of cancer recurrence (Concerns About Recurrence

Questionnaire-3, CARQ-3)

- Timely initiation of adjuvant therapy
- Morbidity including lymphedema, capsular contracture and range of motion (ROM) of the shoulder
- Breast photos
- Recurrence
 - Local recurrence
 - Regional recurrence
 - Distant metastasis
 - Disease-specific survival
 - Overall survival
- Death including cause of death

Concerning cancer related endpoints

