Is measured at abduction/flexion with the patient sitting in front of a poster with a circle with degrees 0-180° (Appendix X).

Capsular contracture

Capsular contracture is measured by Bakers Grading (Appendix X)

Objective evaluation will be done at follow-up before and 1 year after first surgery and at year ½,1,2,3,4,5, and 10 after second operation and stored in the DBCG database under RECON follow-up.

Photos

Frontal and side-photos pre-operatively with arms down and arms up, before first surgery, after first surgery but before start of radiation therapy, and at year 1, 2, 3, 4, 5, and 10. At any event new photos are taken.

The photos will be stored in a database established for that purpose at Aarhus University Hospital.

The guidelines for photos is in Appendix XI.

BREAST-Q and QoL-questionnaires

TREATMENT ARM A/Prospective study	PRE-OP	POSTOP	POST-OP	POST-FINAL
Delayed-immediate INSTRUMENT		2 WEEKS	9-15 MO (pre-final recon) ###	RECON $\frac{1}{2}+1+2+3+4+5+10$ YEARS
DBCRT Recon Questionnaire*	X	X	X	X
BREAST Q** Part I_B	X		X	
BREAST Q Recon ** Part II_B		X	X	X
BDI Becks Depression Inventory**	X	X	X	X
CARQ-3 Concerns About Recurrence Questionnaire -3**	X	X	X	X

* Mandatory Questionnaires

**Optional Questionnaires for Danish patients only. Data can be stored in RedCap

If the patient does not undergo a final reconstruction, they will have the same POST-FINAL RECONS-questionnaires as the ones who do and at the same time-points, but will not have the PRE-FINAL RECON-questionnaire.

TREATMENT ARM B Delayed reconstruction INSTRUMENT	PRE-OP	POSTOP 2 WEEKS	POST-OP 9-15 MO (pre-final recon)	POST-FINAL RECON ½+1+2+3+4+5+10 YEARS
DBCG RT Recon Questionnaire*	X	X	X	X
BREAST Q** Part I_A	X			
BREAST Q** Part II_A		X		
BREAST-Q** Part I_B			X	
BREAST-Q** Part II_B				X
BDI Becks Depression Inven- tory**	X	X	X	X
CARQ-3 Concerns About Recurrence Questionnaire -3**	X	X	X	X

* Mandatory Questionnaires

**Optional Questionnaires for Danish patients only. Data can be stored in RedCap

STATISTICAL CONSIDERATIONS

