According to a study from our group,¹¹ the risk of having complications that lead to surgical interventions was 26% in patients undergoing delayed reconstruction. Thus, the success rate according to the primary endpoint is 74%. We expect a somewhat worse outcome in this study, but we will not accept a deterioration of more than 10% point, corresponding to a success rate of at least 64. In order to show that, the randomized study should include 295 patients in each group (power 80%, type 1 error 5 % [one-sided test], drop-out rate at 3 years 10%). There will be continuous inclusion of patients until patient No. 590 has been followed for 12 months. The estimation of the inclusion period is thus estimated to 5 years.

After an inclusion period of three years 55 patients from one center have been randomized, whereas the expected number is 354 patients. Due to the slow accrual rate and only one center randomizing patients the trial was changed for a prospective trial without randomization and only one treatment arm. The steering committee will consider then inclusion after another two years to decide whether to close the trial or continue.

12 month after end of inclusion in the prospective part, the complication rate for the randomized part will be calculated in the two groups, though acknowledging that there will not be sufficient power for a statistical comparison. In addition, the complication rate for all patients included in arm A with delayed-immediate reconstruction, included after randomization or in the prospective arm, will be calculated. It is anticipated that the complication rate will not exceed 26%, as for delayed reconstruction.

With a the sample size of 178, a one sided exact test will have 80% power to reject the null hypothesis of inferiority, in favor of the alternative hypothesis that the test proportion is non-inferior to the pre-specified standard, assuming that the expected actual proportion is 0,74, the non-inferiority proportion is 0,64 and that the test is made at the 2,5% significance level. With additional centres participating it is expected that a sample size of 178 patients will be reached after additional two years of inclusion

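### With randomisation dropped, change in patient-reported scores from the pre-mastectomy baseline cannot be separated from the course of the cancer, and the protocol plans no use of the randomised arms for these outcomes

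*Protocol*

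**What the plan says.** Under Treatment protocol, the steering committee decided to "change the trial per 30/6-2023 to a prospective trial of arm A without randomization". The Aim compares complications with delayed reconstruction. For patient-reported outcomes it names only one contrast: "patient-reported outcomes will be evaluated postoperatively and compared to preoperative measurements".

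The secondary endpoints include BREAST-Q and "Psycho-oncological endpoints evaluated by validated questionnaires", namely BDI and CARQ-3.

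On timing, Information of the patient states: "Information is given in the plastic surgery clinic when patients are informed about the diagnosis and the treatment plan is discussed with her". It continues: "After her written consent, baseline morbidity evaluation is performed". The questionnaire tables place the first BREAST-Q, BDI and CARQ-3 in a pre-operative column, before the first surgery. Later columns are 2 weeks, 9-15 months (before final reconstruction), and seven time points from ½ to 10 years after final reconstruction. A note to the arm A table says that women without a final reconstruction still receive the post-final questionnaires but not the pre-final one. BREAST-Q, BDI and CARQ-3 are marked optional and for Danish patients only.

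For the randomised patients, Statistical considerations names one analysis by arm: "the complication rate for the randomized part will be calculated in the two groups". It acknowledges that power will be insufficient. Ethical considerations presumes better results and higher satisfaction than with delayed reconstruction when the course is uncomplicated.

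**The concern.** A pre/post change in a single arm contains everything that happens between the two measurements. In arm A that is mastectomy, the first-stage implant or expander, radiotherapy, any chemotherapy, and 6-12 months before the final operation. Mood, fear of recurrence and breast-related quality of life can all move over that period for reasons unrelated to the choice between delayed-immediate and delayed reconstruction. Neoadjuvant therapy is also accepted, so the pre-operative scores may fall at different points of systemic treatment in different women.

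The expectation under Ethical considerations is comparative: higher satisfaction than with delayed reconstruction. The contrast in the Aim is not comparative. A change in either direction could be taken as evidence about the technique when it is not. The protocol also expects the technique to become the national recommendation, so supporting statements about satisfaction may carry weight. Meanwhile the randomised women have a parallel questionnaire schedule, for which the protocol names no comparison by arm.

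**Working it through.** **1. The plan's own figure.** The protocol gives no sample size or precision for patient-reported outcomes. Its single-arm size of 178 belongs to the complication endpoint (success 0.74 against 0.64, one-sided exact test at 2.5%). It reproduces: success is declared at 127 or more of 178, with actual type I error 0.0233 and power 0.815. Nothing below affects that test.

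**2. Which scores can be compared between the randomised arms.** From the two questionnaire tables:

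| Instrument | Pre-op | 2 weeks | 9-15 months | Post-final |
|---|---|---|---|---|
| BDI, CARQ-3 | A and B | A and B | A and B | A and B |
| BREAST-Q, arm A | I_B | II_B | I_B, II_B | II_B |
| BREAST-Q, arm B | I_A | II_A | I_B | II_B |

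- BDI and CARQ-3 match in every column, so they can be compared by arm with adjustment for the pre-operative value.
- BREAST-Q change from pre-op cannot be compared by arm. Arm A starts on Part I_B and arm B on Part I_A, which the Appendix lists as different questionnaires (before reconstruction and before mastectomy). Part II_B is common to both arms only after final reconstruction.
- At 9-15 months, arm A women with no final reconstruction do not complete the questionnaire, and Statistical considerations says that some women kept their primary implant. The arm A respondents are thus selected by a decision made after randomisation, and a comparison by arm at that visit is not protected by it.

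**3. How easily a single-arm change becomes significant with no reconstruction effect.** Suppose the cancer course alone shifts the mean by *s* SD of change. The probability of a significant change in the direction of that shift (two-sided 5%) is Φ(s√n − 1.96). The values of *s* are assumptions; n = 89 stands for half of 178 responding.

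| s | n = 178 | n = 89 |
|---|---|---|
| 0.1 | 27% | 16% |
| 0.2 | 76% | 47% |
| 0.3 | 98% | 81% |
| 0.5 | >99% | >99% |

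For example, at s = 0.2 and n = 178: 0.2 × 13.34 − 1.96 = 0.71, and Φ(0.71) = 0.76. A significant pre/post change is therefore weak evidence about the technique.

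**4. Precision of the randomised contrast.** The protocol reports 55 women randomised after three years and gives no split. Assuming 27 and 28 with full response, the 95% half-width of a standardised mean difference is 1.96 × √(1/27 + 1/28) = 1.96 × 0.270 = 0.53 SD, before any gain from baseline adjustment.

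With equal arms of 27.5, the difference detectable with 80% power is (1.96 + 0.84) × √(2/27.5) = 0.76 SD, and power for 0.5 SD is 46%. At lower completion:

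- 70% (19.25 per arm): half-width 1.96 × √(2/19.25) = 0.63 SD; detectable difference 0.90 SD.
- 50% (13.75 per arm): half-width 1.96 × √(2/13.75) = 0.75 SD; detectable difference 1.07 SD.

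**The case against.** The strongest reply is that the Aim describes and does not attribute. It says that scores will be compared with pre-operative values and claims no effect of the technique. The expectation of higher satisfaction is a presumption in an ethics section; the hypothesis and sample size concern complications only. This stands, and it limits the point to how the change scores may be used.

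A second reply is that the protocol sets out no detailed analysis of any secondary endpoint, which may properly be left to a statistical analysis plan. A reader might infer that the arm B questionnaires will go unused. The protocol does not say so: it keeps their schedule and the intention-to-treat principle. What stands is narrower. The Aim itself fixes a weak contrast, and the only analysis by arm that is named for the randomised part is of complications.

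A reader might also infer that the change reflects the cancer rather than the reconstruction, or that improvement is to be expected regardless. The documents support neither. They do not show that the reconstruction contributes nothing, and they give no direction. BREAST-Q starts before mastectomy in arm A, so later scores could fall.

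Finally, 55 women are few, and the added analysis is unlikely to settle anything. That is true, but the protocol already accepts an underpowered comparison by arm for complications.

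**Conclusion.** The point holds in a limited form. As the trial now recruits, change in BDI, CARQ-3 and BREAST-Q from the pre-mastectomy baseline cannot be separated from the course of the cancer and its treatment. It cannot support a claim of higher satisfaction than with delayed reconstruction. The bias cannot be sized or signed from the documents; the probabilities above are illustrations under assumed shifts.

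The randomised arms offer a contrast protected from this confounding, with a half-width of about 0.53 SD under an assumed 27/28 split and full response. The count of 55 was taken after three years, while randomisation ran for three and a half (1 January 2020 to 30 June 2023), so the final number may be larger. Optional, Danish-only questionnaires may bring non-response bias as well as lower precision.

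These are secondary endpoints and the primary conclusion is unaffected. This is an inexpensive improvement, not a fatal flaw.

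**What to change.** 1. State in the Aim that pre/post changes in BDI, CARQ-3 and BREAST-Q are descriptive and are not evidence about the reconstruction method.
2. Extend the randomised-part analysis in Statistical considerations to report arm A against arm B as randomised, with 95% confidence intervals. Use BDI and CARQ-3 at 2 weeks and at the post-final time points, adjusted for the pre-operative value, and BREAST-Q Part II_B at the post-final time points without change from pre-op. Report the response by arm at each time point.
3. Treat any 9-15 month contrast, between arms or within arm A, as descriptive and limited to women who go on to final reconstruction.
4. The note that keeps women without a final reconstruction in the post-final questionnaires stands with the arm A table only. State whether it also holds for arm B, because the post-final contrast depends on it.

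The cost is wording and one added analysis of questionnaires already scheduled, with no new patients or visits. The price is a weaker claim from the single-arm change scores, and a randomised estimate that is wide and open to non-response bias.

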In the setting of post-mastectomy radiation therapy (PMRT), or any other adjuvant therapy for that matter, it is of utmost importance to choose the safest reconstructive technique in order not to delay adjuvant therapy^{17,18}. This favors a surgical procedure with no donor-site and a simple reconstruction. Several studies on timing of radiation therapy and reconstructive procedures have been published including 3 reviews.¹⁹⁻²¹ These papers systematically review the currently available evidence, describing in-coherent, retrospective, smaller or larger cohorts of patients from multiple centers, who had either implant-based or autologous reconstructions performed on very different time-points in the course of treatment.¹⁹ The patients had, moreover, undergone various radiation protocols (different doses, with or without boost and bolus etc.). In addition, different outcomes are reported in the individual studies, and it is therefore not possible to draw any firm conclusion on which type of reconstructive procedure to prefer

Very recently published studies likewise do not give a clear indication on which type of reconstruction to prefer in patients undergoing radiation therapy as well,²²⁻²⁴ although one of the studies reports acceptable results with autologous immediate breast reconstruction.²³ The long-term oncological outcome after reconstruction and radiation therapy is not well described, but recently the 10-year experience with delayed immediate reconstruction at MD Anderson Cancer Center was published.²⁵ Almost 400 patients were treated with skin-sparing mastectomy and immediate tissue expander placement and subsequent radiation thera-

py. Final reconstruction was performed around 12 months after the primary operation and 7 months after PMRT. Eighty-five percent had a final procedure performed. Thirteen percent had complications and had the expander removed. Five-years loco-regional control and overall survival was 99% and 92%, respectively. Data on target volume definition and radiation therapy technique used as well as cosmetic outcome in this patient cohort are still awaited.

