During the active RCT it was found that some of the included patients did not wish for the delayed (autologous) reconstruction, but rather kept their primary implant. It therefore seems that the rate of capsular contracture is lower than originally expected, perhaps due to a more gentle radiation therapy in the protocol.

For the prospective study, all participants will be included in the analyses, but stratification for type of final reconstruction will be performed.

ETHICAL CONSIDERATIONS

This trial is being conducted according to the 5th version of the Helsinki Declaration. The trial can only start after the approval of the regional ethical committee for Region Midt.

The risk of complications and failure is increased in breast reconstruction after mastectomy in patients who have RT. This is well known but still more and more patients request and receive such procedures.

Patients participating in the present study will be informed that reconstruction combined with RT doubles the risk of complications no matter which treatment arm they belong to. Presumably, delayed-immediate reconstruction will lead to better results and a higher satisfaction to the patients than will delayed, secondary reconstruction if patients have a uncomplicated trajectory. Therefore, if delayed-immediate reconstruction can be performed without increasing other risks, it could turn out to be preferable, and that is what the present study aims to prove.

At present there is no firm evidence and no consensus on which procedure to preferre, but there is an international trend towards primary reconstruction also in this group of patients, and there is a risk that this approach will be routinely adopted before sufficient evidence is available, for which reason it is crucial to first explore this option through a study.

PUBLICATIONS

The results from this study will be published irrespective them being positive, negative, or inconclusive. After approval of the study from the local scientific committee, the study will be registered on www.clinicaltrials.gov according to current recommendations.

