APPENDIX

IIa	DBCG RT RECON Primary endpoints after first surgery
IIb	DBCG RT RECON Primary endpoints after second surgery
III	BDI Becks Depression Inventory
IV	CARQ-3 Concerns About Recurrence Questionnaire-3
V	Breast-Q Part I_A Questionnaire before mastectomy
VI	Breast-Q Part I_B Questionnaire before reconstruction
VII	Breast-Q Part II_A Questionnaire after mastectomy
VIII	Breast-Q Part II-B Questionnaire after reconstruction
IX	DBCG RT RECON Questionnaire (morbidity)
X	DBCG RT RECON Registration form (morbidity and cosmesis)
XI	DBCG RT RECON Manual for clinical photos

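### The primary endpoint window has no defined end for women who keep the primary implant, although they stay in the analysis

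*Protocol*

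**What the plan says.** - **Endpoint.** Protocol, OUTCOME (Primary endpoint): any listed complication that makes surgical intervention necessary, "within a period up to 1 year after the final reconstruction". No other closing date is given.
- **Who is analysed.** TREATMENT PROTOCOL, Treatment arm A: "Patients, who will not have the second delayed procedure performed will be included in the analysis of 'intention to treat' group". STATISTICAL CONSIDERATIONS, on the prospective part: "all participants will be included in the analyses, but stratification for type of final reconstruction will be performed".
- **The group exists.** The same section reports that some women in the randomised phase "did not wish for the delayed (autologous) reconstruction, but rather kept their primary implant". Their number is not given. The background text says of a 10-year expander series: "Eighty-five percent had a final procedure performed".
- **Data capture.** The APPENDIX lists form IIa, "DBCG RT RECON Primary endpoints after first surgery", and form IIb, "DBCG RT RECON Primary endpoints after second surgery".
- **The only rule for women without a final reconstruction.** It is a note to the arm A questionnaire table in REGISTRATION. It gives them the later questionnaires at the same times as the other women, but names no date to count from. Objective evaluations after the first year are timed from the second operation.
- **Test and timing.** STATISTICAL CONSIDERATIONS: one-sided exact test at 2.5%, expected success 0.74, non-inferiority limit 0.64, n = 178, power 80%. The complication rates are calculated 12 months after inclusion ends.

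**The concern.** The endpoint is closed by an operation that part of the denominator never has, so for those women the stated rule cannot be applied. Whoever prepares the data must choose when to stop counting. Unless this is written down, the choice may be made after the results are known, and it may differ between centres.

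Follow-up would also depend on something that happens after registration, namely whether the second operation takes place. In a single-arm test against a fixed limit no control group shares the same counting rule, so any under- or over-counting passes straight into the tested proportion. The result is meant to inform a national treatment recommendation.

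**Working it through.** **1. The plan's own figure.** Exact binomial, n = 178, limit 0.64. The smallest number of successes r with P(X ≥ r | 0.64) ≤ 0.025 is r = 127, that is, at most 51 complications. The exact one-sided alpha is 0.0233 and power at 0.74 is 0.8146. The stated 80% power at 178 therefore reproduces. The 127-of-178 rule is derived here; the protocol does not print it.

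**2. Length of the window.** The questionnaire tables place the assessment before final reconstruction at 9–15 months after first surgery. One year after a final reconstruction at about that time is 9 + 12 = 21 to 15 + 12 = 27 months after first surgery. For women without the operation, at least three readings are possible:

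| Reading | Window from first surgery | Effect on their complication rate |
|---|---|---|
| Retained implant counts as the final reconstruction | 12 months, i.e. 9–15 months shorter than for the others | too low |
| Only events on form IIa count | undefined; ends with whatever that form covers | too low |
| Counting continues without limit | longer than for the others | too high |

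**3. If later events go uncounted.** Let f be the share without a second operation and m the share of their events not counted, with the same true rate in all women. Apparent rate = true rate × (1 − f × m). Both f and m are assumptions. The value f = 0.15 comes from the cited series (100% − 85%); f = 0.30 is a sensitivity value. At a true complication rate of 36%:

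| f | m | Apparent rate | P(at least 127 successes of 178) |
|---|---|---|---|
| 0 | – | 36.0% | 2.3% |
| 0.15 | 0.25 | 34.7% | 5.3% |
| 0.15 | 0.50 | 0.36 × (1 − 0.075) = 33.3% | 10.7% |
| 0.15 | 1.00 | 30.6% | 31.8% |
| 0.30 | 0.25 | 33.3% | 10.7% |
| 0.30 | 0.50 | 30.6% | 31.8% |

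The value m = 1 is an upper bound, because form IIa records events after the first operation. In numbers of women, 178 × 0.15 = 26.7, with 26.7 × 0.26 = 6.9 to 26.7 × 0.36 = 9.6 expected complications among them.

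**4. If counting has no limit.** Suppose longer counting adds 5 or 10 percentage points among 15% of women. An expected rate of 26% becomes 26 + 0.15 × 5 = 26.75% or 26 + 0.15 × 10 = 27.5%. Power falls from 81.5% to 74.7% or 66.9%.

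**5. Analysis time.** If registration is close to first surgery, the last woman registered has about 12 months of follow-up at the planned analysis, whereas her window closes at about 21–27 months. The analysis time and the endpoint definition therefore do not fit each other for late entrants, with or without a second operation.

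**The case against.** **The gap is narrower than it first looks.** A reader might infer that the window never starts for these women, or that their later complications are scored as success. The protocol supports neither. It words the window by its end only, and form IIa registers endpoint events after first surgery for every woman. No section says that later events are ignored; that is one reading among several.

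**The retained implant may be the final reconstruction.** Stratifying all participants by type of final reconstruction allows this reading. Two places speak against it: the questionnaire note treats these women as not having a final reconstruction, and Treatment arm A describes final reconstruction as surgery done after chemotherapy and radiotherapy. The reading would also close their window 9–15 months before that of the others.

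**Case mix is a different matter.** A reader might infer that the pooled rate mainly measures how many women skip the second operation. Take 14–17% complications after the first stage and 26% after the second, with independence assumed. The pooled rate p1 + (1 − p1) × 0.26 × (1 − f) is then 36.4–38.6% at f = 0 and 33.0–35.3% at f = 0.15. This formula has no term for the window. It shows that fewer operations bring fewer complications, which belongs to the strategy under intention to treat. Its inputs are also weak: the 17% rests on 24 women, and neither figure is said to be restricted to complications needing surgery. It is no evidence for the present point, and the planned stratification already goes some way to meet it.

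**The illustration is uncertain.** The cited series also reports 13% with complications and expander removal, so some women without a final procedure may already be counted as failures, and less would be lost. Conversely, the share keeping the implant in this trial is not known and may exceed 15%.

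**Data can be recovered.** Consent gives access to medical records, so events could be found later, and the content of form IIb is not shown. This makes the gap cheap to close but does not say up to which date events count.

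**Conclusion.** The point stands in limited form: the end of the primary endpoint window is undefined for women without a second operation, who are explicitly analysed. This is a defect in what the protocol fixes rather than a detail left for later, because the endpoint itself is tied to an operation that these women do not have.

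Neither the direction nor the size of the bias can be read from the protocol. With 15% lacking a second operation and half of their events uncounted, both assumptions, the chance of passing at a true 36% is 10.7% instead of 2.3%. Open-ended counting instead lowers power, to 67–75% under the additions assumed above. With a defined window for every woman, 178 patients and the 127-success rule stand as planned. The definition should be settled before the primary endpoint is analysed.

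**What to change.** In the primary endpoint definition:

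1. Set a closing date for women without a second operation, counted from first surgery, that gives follow-up comparable to women with both stages. The protocol's own schedule implies about 21–27 months.
2. Count every listed complication requiring surgery up to that date, whether or not a second operation takes place.
3. Have the endpoint form completed at that date for these women.

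In STATISTICAL CONSIDERATIONS:

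4. Reconcile the analysis time with the windows. Either wait until they have closed, or estimate the rate as a cumulative incidence so that incomplete follow-up is handled.
5. Report the rate among women with both stages beside the all-patient rate, using the stratification already planned.

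The window for women with both operations need not change, nor need the sample size. The cost is a few sentences, one added form completion for each woman without a second operation, and possibly a later analysis date. The existing rule for these women covers questionnaires only, so the form completion has to be scheduled explicitly.
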